### **IRB** Protocol

### Multimodal Post-Cesarean Analgesia with Spinal Morphine and Continuous Wound Infiltration of Ropivacaine Using the OnQ® Elastomeric Pump: A Dose-Ranging Study Using a High-Volume, Low-Dose Protocol PI: [name]

Abstract:

The purpose of the proposed study is aimed to determine whether continuous subfascial infusion of ropivacaine using the On-O® elastomeric pump in combination with intrathecal (IT) preservative-free morphine (PFM) will improve post-operative cesarean section pain relative to IT PFM alone (the current standard of care). Using a doubleblinded, randomized, placebo-controlled study design, 60 women undergoing their first, second or third cesarean section will be randomly assigned to one of 3 different groups receiving either saline (control, n=20) or ropivacaine (0.1% or 0.2%, experimental groups n=20 in each) subfascially via the elastomeric pump. We will enroll up to 70 subjects to achieve 60 randomized and treated subjects, to account for screen failures and/or early terminations, All participants will receive an IT dose of 200mcg of PFM as part of a standardized spinal anesthetic for their operative procedure. During closure of their abdomen, all patients will undergo placement of a multi-orifice, silver-impregnated catheter in the subfascial space. At the conclusion of the surgery, the catheter will be bolused with 8ml of one of the three test solutions, after which an On-O® elastomeric pump (containing the same solution as initially administered through the catheter) will be attached to infuse the test solution at a rate of 8ml/hr. The infusion system will then be left in place for up to 72hr. Adjunctive pain medicines (ketorolac, morphine, ibuprofen, and oxycodone-acetaminophen) will be available for the treatment of breakthrough pain during hospitalization. The primary outcome being measured in the study is postoperative pain with movement as assessed immediately after the study bolus (baseline) and during the immediate post-operative period, when leaving the PACU (2hr), 6hr, 12hr, 24hr, 48hr, and 72hr post-op. Pain will also be evaluated by telephone at 4-6 weeks and 3mo after surgery. A visual acuity pain scale (VAPS) will be used to measure patient pain levels while hospitalized whereas pain at the 4-6 week visit and 3mo will be quantitated using a numeric pain scale (NPS). Secondary outcomes to be studied include degree of pain at rest, time to first rescue medication, time to first opioid use, amount of

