# **Objectives:**

The primary outcome measured in this study is post-operative pain with movement measured both during cough and 20° straight leg raise. Pain at rest will also be evaluated. All types of pain will be measured using a visual analogue pain scale (VAPS) determined using a 100mm line with the patient making a mark on the line between no pain and worst pain ever (12). Pain scores will be collected after the bolus of study medication/placebo (zero time), at PACU discharge (2hr), 6hr, 12hr, 24hr, 48hr, and 72hr post-cesarean section. Pain at 4-6 weeks and 3mo will be quantitated over the telephone using a numerical pain scale (NPS) with 0 being no pain and 10 being the worst pain imaginable. In addition to the pain scores, pain with movement will be further evaluated qualitatively using the short-form McGill pain questionnaire (22) at all time-points in the study. This will allow us to look at pain quality (sharp, burning, etc.), as well as examining the affective components (exhausting, fearful, etc.) of the pain.

There are several secondary outcomes of this study that can be divided into rescue medication information, medication side effects, breastfeeding, wound evaluation, patient satisfaction, and cost-analysis.

Rescue medication data will be collected during the hospitalization period (0-72hr). We will note the time to dosing with the first rescue medication for breakthrough pain. After the first rescue medication is given, the patients will be eligible for further doses of IV or

PO pain medicines for continued breakthrough pain as needed (see **Study Design and Methods** section below for specifics). The time to first opioid use for pain will also be recorded whether this entails IV or PO administration. Additionally, we will quantitate narcotic use in terms of morphine equivalents given (in mg) both by post-operative day and with a cumulative total. The total dose of NSAIDs (in mg) will be recorded for each of the first three postoperative days, along with a cumulative total. We will also be measuring the proportion of patients who require opioid supplementation at 0, 2, 6, 12, 24, 48, and 72 hours post-op. We will also ask if patients are still requiring opioids and/or NSAIDs for surgical discomfort along with inquiring about the amount of each used per day at the 4-6 week and 3 month follow-up telephone calls.

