# **Participant Selection**

The study will take place at Emory University Hospital Midtown (EUHM), which cares for a mixed community- and university-based obstetric practice. Parturients will be recruited from the patient pools of both private and Emory physicians, and enrolled after appropriate consent has been obtained. The inclusion criteria for the study includes all ASA class I-III parturients at least 34 weeks pregnant, that are 18 years or older, have never had a cesarean section, have had one or two prior cesarean sections, and are undergoing scheduled or unscheduled non-emergent cesarean sections with spinal anesthesia. Exclusion criteria includes parturients who have allergies to morphine, ketorolac, or amide local anesthetics; pregnancies less than 34wks gestational age; significant maternal cardiac, liver, or renal disease; maternal history of narcotic abuse or dependency; presence of a pre-operative fever ( $\geq 100.4$  °F); emergent cesarean sections with or with-out general anesthesia; and patients in whom valid consent is questionable (non-English speakers or mentally-impaired individuals). Study patients have the option of withdrawing from the study at any point, as the On-Q® pump infusion can be simply discontinued and the catheter removed. At such time the patient would revert to our standard pain management protocol.

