# **Statistical Analysis**

Based on a preliminary sample size calculation using an  $\alpha$  risk of 0.05, a  $\beta$  risk of 0.2, and an effect size involving a 40% reduction in pain scores, we estimate that 20 patients are needed in each arm of the study. Data normality will be tested using the Kolmorgorov-Smirnov test. Normally distributed data will be presented as means  $\pm$  SD, whereas non-normally distributed data will be expressed as medians with interquartile ranges. Categorical data will be reported as frequencies. VAS scores will be analyzed using two-way ANOVA for repeated measures. Non-normal data will be analyzed using the Friedman test. Categorical data will be analyzed using the X test. Multiple comparisons will use a Bonferroni correction. Differences will be considered statistically significant at a P<0.05.

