### **Patient Safety and Potential Benefits**

There is no added discomfort of having the On-Q® device placed, as it is inserted during surgery under spinal anesthesia. There is also minimal to no discomfort upon removal of the catheter which is simply pulled out when the infusion is completed, if the patient withdraws from the study, or if the patient is discharged from the hospital. An adhesive bandage is placed over the insertion site and left in place for 12-24hr after catheter removal. Control patients who end up getting the normal saline infusions will be receive the current standard of care for pain relief at our institution (PFM and adjunctive medications).

IRB00073292

All medications utilized in this study are currently employed on the labor and delivery and postpartum wards at EUHM. The spinal anesthetics described earlier constitute our standard of care for the provision of intraoperative anesthesia for cesarean section. The treatment of post-operative pain with IV ketorolac, and further with IV morphine for unremitting pain, represents our usual standard during the first 24hrs after cesarean delivery. Pain relief on the second and third postsurgical days is commonly provided by our obstetricians using oxycodone-acetaminophen (5/325) and ibuprofen, with IV morphine being occasionally used in refractory cases.

Several of our obstetricians routinely place the OnQ® pain system post-cesarean delivery, and administer 0.5% bupivacaine at 5 ml/hr through a subfascial catheter. In this study, we propose changing the LA infused from 0.5% bupivacaine at 5 ml/hr to either 0.1% or 0.2% ropivacaine, at 8 ml/hr. This change should actually enhance patient safety as not only does this represent a reduction in LA dose/hr (from 25mg/hr with bupivacaine to either 8 or 16mg/hr with ropivacaine, respectively), but also constitutes a change from a relatively cardiotoxic LA (bupivacaine) to one considered significantly less so (ropivacaine) (29). Ropivacaine is widely used in obstetric anesthesia for labor epidurals, and in fact, 0.2% ropivacaine at 8-12ml/hr forms our standard labor epidural infusion at EUHM. Finally, it should be noted that the highest daily ropivacaine dose utilized (day 1 which includes the hourly infusion plus an 8ml bolus (which works out to either 200mg or 400 mg for the two infusions) in this study is well below the maximum recommended daily dose of 800mg (30).

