There are possible benefits of being enrolled in the study. If our hypothesis is correct, both acute postoperative pain (at rest and with movement) and chronic postsurgical pain will be reduced in patients that receive the ropivacaine infusions. These patients would likely experience a reduction in the use of opioids and other adjunctive pain medicines. This could lead to a reduction in the incidence and treatment of medication-related side-effects. The reduction in pain, as well as a decrease in medication use, might result in more successful and safer breastfeeding. Pain and side-effect reduction might also lead to the need for fewer nursing interventions, along with a potential decrease in the length of stay after a cesarean section. If these goals are met, this truly multimodal technique of postoperative pain control might also decrease the cost of these patients' hospitalization.

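### The planned VAPS tests have no rule for missing scores, and in standard form they drop a woman who lacks a 72 h score; the loss may be small, and a mixed model avoids it

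*Combined protocol and SAP*

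**What the plan says.** The primary outcome is pain with movement, scored on a 100 mm VAPS during both cough and straight leg raise. The Objectives section schedules it at seven in-hospital times: just after the study bolus, then at 2, 6, 12, 24, 48 and 72 h.

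The Statistical Analysis section states that "VAS scores will be analyzed using two-way ANOVA for repeated measures" and that "Non-normal data will be analyzed using the Friedman test". It adds a Bonferroni correction for multiple comparisons. Neither that section nor any other gives a rule for missing scores, an imputation method or an analysis population.

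Four other places bear on whether scores can be missing:

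- Abstract: the VAPS "will be used to measure patient pain levels while hospitalized". Later pain is collected by telephone on a different, numeric scale.
- Participant Selection: "Study patients have the option of withdrawing from the study at any point".
- Patient Safety and Potential Benefits: the catheter is "simply pulled out when the infusion is completed, if the patient withdraws from the study, or if the patient is discharged from the hospital".
- Abstract, on enrolment: "We will enroll up to 70 subjects to achieve 60 randomized and treated subjects, to account for screen failures and/or early terminations".

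Against these, the Objectives section treats the inpatient period as 0 to 72 h: "Rescue medication data will be collected during the hospitalization period (0-72hr").

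**The concern.** Repeated-measures ANOVA in its textbook form, and the Friedman test, work on complete rows with one value per woman at every time. If one value is absent, software either drops the woman or does not run. A woman discharged after 48 h would take six observed scores per manoeuvre out of the overall test. One who withdraws after 12 h would take out four. The trial has only 20 women per arm, so there is little power to spare.

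Two further points follow from the same sentences.

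- The plan does not say whether a form that accepts incomplete rows is meant. The choice could therefore be made after the data are seen.
- Friedman ranks the times within each woman, and the arm does not enter the calculation. If the data are judged non-normal, the named test would not address the primary hypothesis even with complete data. No between-arm rank test is named in its place.

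Loss could also be related to pain. The protocol hopes for "along with a potential decrease in the length of stay after a cesarean section". If women with less pain go home before 72 h, the women left with complete rows are not a random subset.

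**Working it through.** **1. The plan's own figure.** The inputs in Statistical Analysis are alpha 0.05 (two-sided assumed), power 80% and a 40% reduction, giving 20 per arm. No control mean or SD is given, so the figure cannot be reproduced directly. Working backwards by the normal approximation, the standardised effect is d = (1.960 + 0.842) × √(2/20) = 0.886. This implies SD / control mean = 0.40 / 0.886 = 0.45. Forwards, n = 2 × (1.960 + 0.842)² × (0.45 / 0.40)² = 19.9, which rounds up to 20. The figure is attainable under that assumption, which is used below.

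**2. Do the tests need complete rows?** One 72 h value was removed from an artificial data set of 10 subjects at 7 times. A standard repeated-measures ANOVA routine stopped because the data were unbalanced. A standard Friedman routine returned no result until the whole subject was dropped, leaving 9.

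**3. Scores discarded, per manoeuvre.** Scheduled: 3 × 20 × 7 = 420. The loss rates are assumed, because the documents give none.

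| Women without 72 h score | Observed scores | Discarded | Share |
|---|---|---|---|
| 5% (1 per arm, 3 in all) | 420 − 3 = 417 | 3 × 6 = 18 | 4% |
| 10% (2 per arm, 6 in all) | 420 − 6 = 414 | 6 × 6 = 36 | 9% |

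Counting cough and leg raise together doubles both counts and leaves the shares unchanged.

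**4. Power on complete rows, random loss, no replacement.** The comparison is one ropivacaine arm against saline with three-arm pooled error. The true difference is taken as 20 mm (40% of an assumed 50 mm). The SD of a woman's mean score, 22.19 mm, is set so that 20 per arm gives 80%. Noncentrality is 20 / (22.19 × √(2/n)), with 3n − 3 df.

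| Complete per arm | Noncentrality | df | Power at 0.05 | Power at 0.025 (Bonferroni, two comparisons) |
|---|---|---|---|---|
| 20 | 2.85 | 57 | 80.0% | 70.7% |
| 19 | 2.78 | 54 | 77.9% | 68.1% |
| 18 | 2.70 | 51 | 75.6% | 65.4% |

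The normal approximation agrees. For n = 19, 0.886 × √(19/2) − 1.960 = 0.771, or 78.0%. For n = 18 it is 0.698, or 75.7%.

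**5. Direction of bias if low pain drives early discharge.** This was simulated with 20 women per arm and seven correlated scores bounded at 0-100 mm. Arm means were 50 and 30 mm and SD about 27.5 to 27.8 mm. Loss of the 72 h score was 10% overall, made likelier by a low 48 h or 72 h score. The complete-row analysis of the seven-time mean estimated 19.4-19.8 mm for a true 20 mm, with power of 73-74%. A mixed model on all observed scores kept 79-80% power and estimated 19.7-20.1 mm; that range also covers heavier loss, up to 25%. With no true effect, both rejected in 4.6-5.3% of runs.

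**The case against.** The strongest reply is that little may be lost.

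- **The stay is planned to 72 h.** LATCH scoring, wound checks, the satisfaction score and rescue-drug recording all run to 72 h. The sentence on catheter removal lists occasions for removal and does not predict early discharge. This stands, and it is why the loss can only be given as an assumed range. A reader might infer heavy loss, such as a quarter of women, but nothing in the documents supports that rate.
- **The plan does not prescribe dropping women.** A repeated-measures ANOVA can be fitted in general linear or mixed-model software that accepts incomplete rows. A woman's scores could also still enter summaries and comparisons at single times. This stands too: what is at risk is her place in the overall test, not every use of her scores. It does not remove the gap, because the plan does not say which form will be used.
- **Over-enrolment covers it.** With up to 70 enrolled, a woman who withdraws might be replaced, and the power loss above would shrink. But the target is women randomised and treated, and a woman missing only her 72 h score is both. Replacement would also not restore the scores discarded.
- **Any bias is conservative.** Correct in the case examined, where false positives were not inflated. A reader might infer a risk of a spurious benefit, and the calculation does not support that.

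The power figures do not apply to the Friedman route. Its larger fault is that it does not compare the arms.

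**Conclusion.** The point holds as a worthwhile, inexpensive improvement and not as a flaw that undermines the trial. The plan leaves open what happens to a woman with incomplete VAPS scores. The standard form of both named tests would remove her from the overall analysis, and the non-normal fallback does not test the arms.

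At an assumed 5-10% of women without a 72 h score and no replacement, the cost is 4-9% of observed scores per manoeuvre and about 2 to 4 points of power (80% to 78-76%). If low pain drives the loss, 10% would shrink a 20 mm difference by under 1 mm. These sizes rest on the assumed loss rate, a 50 mm control mean and an SD back-solved to give 80% power. Only the mechanism and the missing rule come from the documents.

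**What to change.** For VAPS, replace both the ANOVA and the Friedman fallback with a mixed model for repeated measures. Fit arm, time and arm × time, with an unstructured or heterogeneous covariance and small-sample degrees of freedom. Use all observed scores from every randomised woman who received the study bolus, analysed as randomised. In addition:

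- Fit the model to each movement manoeuvre, or to one named in advance.
- Name the primary arm contrast, for example each ropivacaine arm against saline averaged over the post-bolus times, with the Bonferroni correction already planned. Say whether the zero-time score, taken just after the bolus, enters that average.
- Handle non-normality by transformation, or by a robust or rank-based between-arm sensitivity analysis that keeps partly observed women.
- State that a woman who received the bolus stays in the analysis even if she stops early.

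The mixed model assumes that loss depends only on observed scores. A movement VAPS at any discharge before 72 h would help to test this, but it is optional.

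The cost is a few sentences in the plan and slightly more analysis work in standard software. The sample size does not change.

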To date, long-acting neuraxial opioids like PFM provide the gold standard for postcesarean delivery analgesia whether given via the IT or epidural route, providing excellent pain relief for the first 24hr while allowing the mother to ambulate and care for her child (18, 19). However, it is clear that neuraxial opioids do not provide complete analgesia for cesarean section when used as primary agents, with more than 70% of patients requesting further analgesia (19). Even when codeine with acetaminophen is given prn, 33% of women in one study still experienced inadequate analgesia (18). Pain with movement appears to be the most poorly treated pain phenomenon using neuraxial PFM (19). Again, this points to the importance of multimodal pain control in obstetric patients. Surprisingly, while continuous wound infiltration has been examined as a primary technique for post-cesarean pain relief (13,14,15,16) and has even been compared for efficacy to epidural (13,14) and IT (17) post-cesarean analgesia, no one has tested to see if continuous wound infiltration with LAs improves the analgesia obtained from IT PFM. However, it is standard practice of some obstetricians in our institution to use the continuous wound infiltration system on every patient undergoing a cesarean section whether they have IT PFM or not. The purpose of the proposed study is to examine the hypothesis that continuous wound infusion with ropivacaine using a highvolume, low-dose protocol will significantly improve pain with movement after cesarean section in patients who have received our standard dose of IT PFM. A control group (IT PFM + saline wound infusion) will be compared to two groups receiving both IT PFM along with one of two doses of ropivacaine (experimental groups) using the OnQ® elastomeric pump for delivery of the infusions. We have purposefully used lower concentrations of ropivacaine (0.1-0.2%) along with higher volumes in recognition that the nerves to be anesthetized are of smaller diameter, and therefore require lower concentrations of LA for this effect; while ensuring a high enough volume to completely

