### **Study Design and Methodology**

After informed consent has been obtained, all study participants will receive spinal anesthetics based on their height to provide anesthesia for their cesarean sections as per our usual clinical practice. Patients  $\geq 64$  inches will get spinal anesthetics containing 12mg 0.75% bupivacaine (1.6ml), 10mcg fentanyl (0.2ml), and 200mcg PFM (0.4ml) for a total volume of 2.2ml. Patients  $\leq 63$  inches will receive the same spinal anesthetic as those  $\geq 64$  inches except that the dose of 0.75% bupivacaine be reduced to 10.5mg (1.4ml) resulting in a total volume of 2.0ml. The PFM dose of 200mcg was chosen as it is the commonly used clinical dose (28). These spinal anesthetics reliably provide anesthesia for 1.5-2hr in each patient population. The patients will have been randomly assigned to one of three study arms prior to initiation of the anesthetic using a computer generated random number list. The randomization list has already been created using a randomization free-ware packet from the internet (Random Number Generator,

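### Friedman, the only test named for non-normal data, cannot compare the three parallel arms, so continuous outcomes measured once have no usable between-arm test and repeated non-VAS scores have none if judged non-normal

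*Combined protocol and SAP*

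**What the plan says.** The Statistical Analysis section is the whole analysis plan. It starts with a Kolmogorov-Smirnov check of normality and then assigns tests. For pain scores, "VAS scores will be analyzed using two-way ANOVA for repeated measures". Then, without naming an outcome, "Non-normal data will be analyzed using the Friedman test". Categorical data go to chi-square. Multiple comparisons get a Bonferroni correction, but no pairwise test is named. There is no one-way ANOVA, t-test, Kruskal-Wallis, rank-sum or log-rank test.

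The design is parallel. Under Study Design and Methodology, "The patients will have been randomly assigned to one of three study arms prior to initiation of the anesthetic". The Introduction and Background section states the contrast of interest: "A control group (IT PFM + saline wound infusion) will be compared to two groups" given ropivacaine.

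The Objectives section lists continuous outcomes other than VAS scores:
- "we will quantitate narcotic use in terms of morphine equivalents given (in mg) both by post-operative day and with a cumulative total"
- NSAID mg is summed in the same way, per day for three days and overall.
- "We will note the time to dosing with the first rescue medication for breakthrough pain"; the time to first opioid is recorded as well.
- Satisfaction is scored once, on a 100 mm scale at 72hr.
- The short-form McGill is completed at every time-point, and LATCH is scored in the PACU and then once per shift.

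**The concern.** Friedman compares related measurements within a block. Here the only natural block is the woman, and she belongs to one arm, so every within-woman comparison is between occasions and none is between treatments. A plan that sends non-normal data to this test has no comparison of ropivacaine with saline for those data.

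The exposed outcomes include the amounts and timing of rescue opioid and NSAID, and satisfaction. Lower opioid use and higher satisfaction are benefits the protocol says it expects. Two things could go wrong. The between-arm test might be picked once results are visible. Or Friedman might be run on daily totals and a significant result, which reflects only change from day to day, be reported as if it concerned treatment.

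**Working it through.** **1. Match each outcome to the named tests.**

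| Outcome | Values per woman | If judged non-normal | If judged normal |
|---|---|---|---|
| Cumulative opioid mg, cumulative NSAID mg, 72hr satisfaction, time to first rescue, time to first opioid | 1 | Friedman: cannot be computed | No test named |
| Daily opioid and NSAID mg, short-form McGill, LATCH | Several | Friedman: tests occasions, not arms | No test named |
| VAPS with movement (primary) and at rest | 7 in hospital | Unclear: ANOVA or Friedman | Repeated-measures ANOVA |
| Categorical, including the proportion requiring opioids | – | Chi-square | Chi-square |

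**2. One value per woman.** With n women, k values each and rank sums R_j, the statistic is

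Q = 12 / [n k (k+1)] × ΣR_j² − 3n(k+1), on k−1 degrees of freedom.

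With n = 60 and k = 1, each woman's only value has rank 1, so R = 60 and Q = 12/(60×1×2) × 60² − 3×60×2 = 360 − 360 = 0 on 0 degrees of freedom. Standard software refuses to run it and asks for at least 3 related samples.

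**3. Several values per woman.** If a woman's daily amounts satisfy a > b > c, then 0.6a > 0.6b > 0.6c. Her ranks are unchanged, and so is Q. On one simulated log-normal data set of 60 women by 3 days, multiplying both ropivacaine arms by 0.6 or by 0.1 left Q at exactly 32.03. On a simulated set of 7 pain times, Q was 209.73 both with no arm effect and after a 40% cut in both ropivacaine arms.

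**4. Workarounds.** Lining up unrelated women across arms as if matched gave p from 0.0002 to 0.55 on one simulated data set, depending only on row order. Using arm medians with time-points as blocks gave a type I error of about 0.41 at a nominal 0.05 (assumed within-woman correlation 0.5).

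**5. VAPS under each reading.** Simulation with skewed scores, log-SD 0.6, correlation 0.5 and 20 per arm (all assumed except the 20):
- ANOVA arm term: type I error 4.9% with a flat time profile and 5.0% with a time trend; power 94% for a constant 40% reduction (72–100% over log-SD 0.4–0.8 and correlation 0.3–0.7).
- Reduction only from 12hr onward: the arm term has 45% power and the arm-by-time term 89%, so both are needed.
- Friedman: rejects 5.5% with no effect and 4.9% with a constant 40% reduction (flat profile), and 100% in both cases with a time trend.

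**6. What a usable test offers at 20 per arm.** The plan's 20 comes from α 0.05, β 0.2 and a 40% reduction, but it gives no SD. Inverting, d = √[2(1.96+0.84)²/20] = 0.886, so SD/control mean = 0.4/0.886 = 0.45. The 20 can therefore be neither confirmed nor refuted, and this point does not depend on it. Kruskal-Wallis power for values 40% lower in both ropivacaine arms, log-normal data:

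| Log-SD (assumed) | No zeros | 30% zeros in every arm |
|---|---|---|
| 0.6 | about 74% | about 23% |
| 0.8 | about 51% | about 16% |
| 1.0 | about 34% | about 12% |

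For normal data with SD 40, 50 and 60% of the control mean (assumed), Kruskal-Wallis has 88, 69 and 52% power against 90, 71 and 55% for one-way ANOVA, a loss of about 2–3 points.

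**The case against.** The strongest reply has four parts.

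*The important comparisons are covered.* VAS scores are sent to repeated-measures ANOVA by name and without condition, which protects both movement and rest pain. The proportion of women requiring opioids at each time-point is categorical and goes to chi-square. This stands as far as it goes, so the plan does not lack every opioid-sparing comparison. The gap is in amounts, times and scores.

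*The primary is therefore safe.* This is not settled. The section runs normality check, then ANOVA, then Friedman for non-normal data, and that order also fits Friedman as the fallback for VAS scores. A reader might equally infer that the primary analysis has lost its arm comparison. That too goes beyond the text, because it needs the Friedman sentence to override the ANOVA sentence and normality to be rejected.

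*Any statistician would use Kruskal-Wallis.* Probably, but that departs from the written plan. It need not be a post hoc choice if it is fixed by amendment before unblinding.

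*The censoring problem is small.* Its size is unknown. The Introduction and Background section reports "more than 70% of patients requesting further analgesia", and a reader might infer that at most 30% of women will have no event. The documents do not support that. The figure comes from a cited source on neuraxial opioids as primary agents and concerns any further analgesia. In this trial ketorolac is the first rescue drug, so a woman can be rescued without ever receiving a rescue opioid.

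**Conclusion.** The concern holds, and it is an error in the named method rather than missing detail. For the five continuous outcomes measured once, no usable between-arm test exists whichever way the normality check falls. For daily mg, McGill and LATCH, the test named for the non-normal case answers a question about time. Neither conclusion rests on an assumed number. Both follow from the design and the definition of the test.

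Three limits apply. VAPS with movement and at rest is affected only if the Friedman sentence overrides the ANOVA sentence. Categorical outcomes are not affected. Women with no rescue or no opioid have censored times, which neither branch handles, but the documents do not give their share.

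The power figures are illustrations on assumed SDs and assumed shares of zeros. They describe the replacement test, not the defect. They also show that if many women use no opioid, even a correct test has little power at 20 per arm. This should be fixed: it bears mainly on the secondary evidence, and the repair is cheap.

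**What to change.** Amend the Statistical Analysis section before unblinding:
- Delete the Friedman sentence.
- State that VAPS is analysed by repeated-measures ANOVA with arm, time and arm-by-time terms, whatever the normality result.
- For every continuous outcome measured once (other than the two times), use Kruskal-Wallis, then a Wilcoxon rank-sum test of each dose against saline with Bonferroni adjustment (0.05/2 = 0.025 each).
- For daily opioid and NSAID mg, test the cumulative total and report the days descriptively.
- For short-form McGill and LATCH, apply the same rank test to one summary per woman, for example the mean over the scheduled assessments.
- For times to first rescue and first opioid, use log-rank, censoring women with no event at 72hr or at earlier discharge or withdrawal. Note that such censoring may be related to pain.
- Let the normality check choose only the summary statistics.

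The cost is a few lines, with no new data and no extra patients. The rank tests give up about 2–3 points of power if data are normal, and they do not estimate a mean difference, so a median difference with its interval should be reported alongside.
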